### *Hyperandrogenemia as a Precursor for PCOS*

Excess androgen production during adolescence is thought to be a precursor of adult PCOS. Women with PCOS often report a history of irregular menstrual cycles during adolescence. A study of girls with menstrual irregularities showed that while some subjects normalized endocrine function as they mature, the majority maintained hyperandrogenism along with the elevated LH levels and polycystic ovaries characteristic of PCOS (Venturoli et al. 1987). Adolescent hyperandrogenemia has also been shown to be associated with higher androgen levels and lower fertility rates in adulthood (Apter and Vihko 1990).

The origin of adolescent hyperandrogenemia is unclear. Along with primary adrenal, ovarian, and neuroendocrine abnormalities, obesity has recently been suggested to play an important role. Several studies have shown a correlation between body mass index (BMI) and androgen levels in adolescent girls. Elevated BMIs are associated with increased total testosterone levels and decreased SHBG levels, leading to marked elevations in free testosterone (Wabitsch et al 1995, Reinehr et al 2005, [name] et al 2006). Androgen levels decrease with weight loss, demonstrating the importance of obesity as a contributing factor (Wabitsch et al 1995, Reinehr et al 2005). The link between obesity and elevated total and free testosterone concentrations is especially concerning in light of the rising incidence of childhood obesity. The most recent data from the National Health and Nutrition Examination Study (NHANES) estimates that 15.1% of girls aged 6-19 years are overweight (defined as BMI  $\geq$  95th percentile on the sex-specific BMI-for-age growth chart) (Hedley et al 2004). Given that obesity is associated with hyperandrogenemia, and adolescent hyperandrogenemia often progresses to adult PCOS, there is concern that the epidemic of childhood obesity may be followed by a rise in the incidence of PCOS.

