Note: Subjects who have just completed IRB-HSR# 8588/ JCM010 will be allowed to consent for JCM021 8 weeks after completing JCM010 (IRB-HSR# 8588). In addition, screening laboratory results from JCM010 (ie. CBC, Chem 17 including LFTs, prolactin, LH, FSH, E1, E2, P, total T, androstenedione, 17-OHP, DHEA-S, fasting insulin, glucose, TSH, hCG, cholesterol, LDL and HDL) may be used as the baseline screening results for this study unless  $> 3$  months have occurred between completion of JCM010 and enrollment in JCM021. If  $> 3$  months have occurred between completion of JCM010 and enrollment in JCM021, then subjects will need to complete all of the screening labs for JCM021. Subjects enrolling in JCM021 8-12 weeks following completion of JCM010 will have blood drawn for a comprehensive metabolic panel and pregnancy test, and may begin flutamide administration immediately upon confirmation that the AST/ALT is within the normal range and the pregnancy test is negative.

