### 2.2 List by bullet format a summary of safety tests/procedures/observations to be performed.

- Sterile technique will be used.
- Before participation in the studies, all participants will be required to have a normal hemoglobin ( $\geq 11.5$  g/dl for non-African American subjects, and  $\geq 11.0$  for African American subjects). Hemoglobin levels will be measured prior to every admission; if the hemoglobin level is  $<11.5$  g/dl for non-African American subjects or  $< 11.0$  g/dl for African American subjects, the study will be discontinued.
- Blood loss will be carefully recorded and limited to a maximum of 7cc/kg (10% of estimated total blood volume) in 8 weeks. As a total of  $< 225$  ml of blood will be drawn during the study (including estimated waste from frequent blood draws), girls weighing less than 32 kg will not be able to participate. Iron supplementation (325 mg once or twice a day dependent on weight) will be prescribed to all participants.
- In order to participate, subjects will be required to have normal transaminases (AST/ALT). Transaminase levels will be checked every week while the subject is on flutamide. If the transaminase levels rise above normal range (AST  $> 35$  U/L or ALT  $> 55$  U/L), the flutamide will immediately be discontinued and liver function tests will be monitored at least weekly until the levels normalize. Should the abnormalities persist or escalate, the subject will be referred to a hepatologist.
- The subjects will be advised to discontinue flutamide and immediately contact the study coordinator should any symptoms of liver dysfunction develop (right upper quadrant pain, anorexia, unexplained flu-like symptoms, jaundice, dark urine, pruritis).
- We will warn participants against becoming pregnant during the study. We will require that sexually active subjects use effective double barrier methods of birth control as needed during the study.  $\beta$ -hCG levels will be measured at screening, immediately prior to initiation of study drug, and weekly while the subject is on the hormonal study drugs; if the  $\beta$ -hCG is positive, the study will be discontinued.

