**Consenting Process:**

An outpatient consenting and screening visit is scheduled for volunteers who express interest in the study. Copies of the approved consent and assent forms are sent to potential subjects beforehand, and we request that the volunteer and her parents review and discuss the forms prior to the screening visit.

The consent and screening visit is held in an outpatient examination room in the CRU. This allows a private conversation between the screening physician and/or study coordinator, the potential participant, and at least one of her parents if the participant is < 18 years of age (other individuals such as family members are allowed in the room if desired by the potential participant). The screening visit usually occurs in the morning, although rarely it will occur in the afternoon. The aims, procedures, and potential risks of the study are first explained by the study physician. Importantly, the potential participant and her parents are given an opportunity to ask any questions, and concerns are addressed. In cases where the potential participant wants to begin the study and her parents concur, the participant, parents, and physician and/or study coordinator sign the consent form. In cases where only one parent is able to come to the screening visit, we allow the second parent to sign the form in advance of the visit. This is done in conjunction with a conversation during which we offer that parent an opportunity to ask any questions and confirm that they understand the study and are willing for their daughter to participate. We routinely inform potential participants verbally that signing the consent form does not compel them to continue participation in the study. The remainder of the outpatient screening visit (i.e., history, physical, screening blood tests) occurs immediately thereafter. Participants generally begin the main part of the study within 1-2 months of the screening visit.

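### Roll-over girls can start flutamide with androgen and hemoglobin eligibility resting on blood drawn before JCM010, because the reuse limit counts time since JCM010 ended, not sample age

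*Combined protocol and SAP*

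**What the plan says.** The relevant text is the note on JCM010 completers under Outpatient Consent and Screening.

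- **Earliest entry.** A girl who has just finished JCM010 "will be allowed to consent for JCM021 8 weeks after completing JCM010".
- **What may be reused.** A listed set of JCM010 screening labs, which includes the CBC and total testosterone but not SHBG, "may be used as the baseline screening results for this study unless" more than 3 "months have occurred between completion of JCM010 and enrollment in JCM021". Beyond that limit she repeats the full JCM021 screening panel.
- **What is redrawn inside the limit.** "Subjects enrolling in JCM021 8-12 weeks following completion of JCM010 will have blood drawn for a comprehensive metabolic panel and pregnancy test". Flutamide may start once AST/ALT is normal and the pregnancy test is negative.

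Other sections bear on this:

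- Inclusion/Exclusion Criteria require hyperandrogenemia (total testosterone above 0.4 ng/mL, or free testosterone above 35 pmol/L) and a minimum hemoglobin.
- The Day Minus 14 to Minus 16 draw is again a metabolic panel and pregnancy test only.
- Data and Safety Monitoring Plan 2.2 states: "Before participation in the studies, all participants will be required to have a normal hemoglobin". It also requires a hemoglobin before each admission.
- Study Design: Biomedical, item 1, describes JCM010 as the same study without flutamide.
- The Consenting Process section says of the present study: "Participants generally begin the main part of the study within 1-2 months of the screening visit".

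**The concern.** The time limit does not measure what it needs to control. A qualifying sample gets older from the day it is drawn, but the 3 months start only when JCM010 ends. The gap from JCM010 screening to its first admission, and JCM010 itself, go uncounted. If JCM010 followed the same procedures, the reused sample also predates 7 days of estradiol and progesterone and two frequent-sampling admissions.

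The androgen criterion carries more weight because it defines the study population. The next scheduled testosterone is at the Day 0 admission, after 14 days of flutamide. So for a girl on the short route, JCM021 itself generates no off-flutamide androgen value. If her androgens had returned to normal in the meantime, her progesterone sensitivity would still be counted in the flutamide group and compared with historical controls, and no concurrent arm would reveal the problem.

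For hemoglobin, the stake is a girl who starts flutamide, is found below the threshold at the pre-admission check, and leaves without endpoint data.

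**Working it through.** The 3-month limit is a rule, not a derived figure, so there is nothing in the plan to reproduce. The check is how old a reused sample can be under that rule.

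**Inputs**
- *g*: JCM010 screening draw to JCM010 first admission. Not documented. Assumed 1-2 months (30-61 days), as the Consenting Process section gives for this study; 0-61 and 0-30 days are also tried.
- JCM010 first admission to completion: about 8 days (7 days of hormones plus the second admission). Assumed from this protocol's schedule.
- *w*: JCM010 completion to JCM021 enrollment. 56 days (8 weeks) to 84 days (12 weeks), or about 91 days at the 3-month limit.
- 3 months = 91.3 days.

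**Formula:** age at enrollment = *g* + 8 + *w*.

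| *g* (days) | *w* = 56 | *w* = 84 | *w* = 91 |
|---|---|---|---|
| 0 | 64 | 92 | 99 |
| 30 | 94 | 122 | 129 |
| 61 | 125 | 153 | 160 |

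With a 1-2 month gap the range is 94-153 days on the 8-12 week route, and up to 160 days at the full 3 months. Every combination exceeds 91.3 days.

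**Shorter gaps.** A sample is under 3 months old only if *g* + (*w* - 56) is below 91.3 - 8 - 56 = 27.3 days. Taking *g* and *w* as independent and uniform (an assumption), with *w* spread over 56-84 days:
- *g* on 0-60.9 days: share under 3 months = (27.3² / 2) / (60.9 × 28) = 372.6 / 1705.2 = 22%, so about 78% exceed 3 months (simulated median about 108 days).
- *g* on 0-30.4 days: 372.6 / (30.4 × 28) = 372.6 / 851.2 = 44%, so about 56% exceed 3 months (simulated median about 93 days).

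**Next checks after the short route**
- Testosterone: Day 0, after 14 days of flutamide.
- Hemoglobin: Day 0, or 1-5 days earlier for a hotel stay, so after 14 - 5 = 9 to 14 days of flutamide. It gates the admission.

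**If the limit ran from the blood draw instead.** Reuse would need *g* of at most 91.3 - 8 - 56 = 27.3 days at 8 weeks, or 91.3 - 8 - 70 = 13.3 days at 10 weeks. At 12 weeks it is impossible, since even *g* = 0 gives 92 days. With a 1-2 month gap, no girl could reuse her labs.

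**Two mismatches in the note**
- Reuse is allowed to about 91 days, but the abbreviated redraw is described only to 84 days. About 7 days are left undefined, although the Day Minus 14 to Minus 16 draw still applies.
- SHBG is in the JCM021 screening list but not in the reusable JCM010 list. A free testosterone calculated from SHBG could not be derived from the listed labs.

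**The case against.** There is a serious case on the other side.

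- **Other off-flutamide values may exist.** If JCM010 was procedurally the same, its Day 0 admission produced serial testosterone and a 6 AM SHBG before its hormones, about 8 + 56 = 64 to 8 + 91 = 99 days before JCM021 enrollment. This stands, and it rules out saying that only the screening value is available. But the note does not make those values part of eligibility or baseline, and they too precede JCM010's hormones. SHBG is also unnecessary for a girl who qualifies on total testosterone.
- **Hemoglobin is protected elsewhere.** It gates each admission. The 8-week wait matches the blood-loss window in Data and Safety Monitoring Plan 2.2, and iron is prescribed. This stands. A reader might infer that girls undergo frequent sampling on an outdated hemoglobin; the documents rule that out.
- **Scope is narrow.** Reuse is permitted, not required, and only within 3 months of JCM010. The recruitment letter reaches girls up to a year out, and later entrants repeat everything. This stands; the number affected could be zero.
- **New recruits also start flutamide without a repeat androgen or hemoglobin.** True, but their screening sample does not have JCM010's hormones and blood sampling between it and flutamide.

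Two stronger readings are tempting. One is that even the earliest permitted entry uses labs over 3 months old. That needs a JCM010 gap of about 27 days or more; JCM010's protocol is not available, and a shorter gap gives 64 days. The other is that normalized girls bias the result. The Background does say that "while some subjects normalized endocrine function as they mature", but it adds that most stayed hyperandrogenic, it concerns girls with menstrual irregularities, and it gives no rate over three to five months. One girl is 1/13 = 8% of the planned group, but that is an illustration, not an estimate.

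**Conclusion.** The point holds as a gap in the eligibility rule. The text of the note establishes it directly: sample age is not limited, and the short route to flutamide rechecks neither the androgen nor the hemoglobin criterion. That the reused values predate JCM010's hormones and sampling follows from the protocol's description of JCM010.

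The figure of about 94-160 days rests on JCM010 having had a 1-2 month screening-to-start interval and an 8-day main part. That most reused samples exceed 3 months survives the shorter gaps tried (78% and 56%), given uniform timing.

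The androgen criterion is the substantive part. The hemoglobin part is limited to 9-14 days of avoidable flutamide and a lost subject. The documents give neither the number of roll-over girls nor a rate of normalization, so no size can be put on any bias. The change is worth making because it is cheap and secures the criterion that defines the population.

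**What to change.** In the JCM010 note under Outpatient Consent and Screening, add total testosterone, SHBG and hemoglobin to the pre-flutamide draw already taken from girls entering at 8-12 weeks. Confirm the androgen and hemoglobin criteria already in the Inclusion/Exclusion Criteria on that draw, and record it as the off-flutamide JCM021 baseline. This adds no threshold and changes no dose.

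Reconcile the note with the Inclusion/Exclusion Criteria, the screening panel and Data and Safety Monitoring Plan 2.2. This should cover SHBG's absence from the reusable list and the difference between the 8-12 week and 3-month windows.

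Running the 3 months from the JCM010 blood draw is an alternative to this, not an addition. In most cases it would end reuse and require the full fasting screening panel, which costs considerably more.

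Cost of the recommended change: a few mL of blood at an existing draw, possibly some days' wait for the hormone results, and a few screen failures that come earlier than they otherwise would. No new visit is needed.

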#### Day Minus 14 to Minus 16: Outpatient blood draw

Blood will be drawn for a stat comprehensive metabolic panel and pregnancy test. The results from

## IRB-HSR#12632: Effect of Androgen Blockade on Sensitivity of the GnRH Pulse Generator to Suppression by Estradiol and Progesterone in Hyperandrogenic Adolescent Girls (JCM021)

these tests should be back within 1 hour. In order to continue with the study, the AST/ALT must be within the normal range and the pregnancy test must be negative. The subject can obtain her study drug as soon as the normal results are confirmed. She can either wait for the results and pick up the flutamide during the same visit, or she can return within the next 2 days to pick up the medication.

### **Day Minus 14: Start Flutamide**

The subject will begin taking flutamide. Subjects weighing  $\geq 50$  kg will receive 250 mg orally twice a day, and subjects weighing  $< 50$  kg will receive 125 mg orally twice a day.

### **Day Minus 7: Outpatient blood draw**

Blood will be drawn to check AST and ALT levels, as well as a serum pregnancy test.

### **Day 0: First inpatient admission**

The subject will be admitted to the CRU, alternate UVA hospital unit, or hotel at 1700 hr and an IV will be placed in a forearm vein. In general, parents are welcome to stay with their child at the off-site hotel if they wish. If the overnight portion of the study is to be done at an off-site hotel, the subject may stay without a parent or legal guardian, as long as two CRU staff are present. Whether or not a parent needs to remain during the overnight admission will be discussed when the visit is scheduled. A small amount of topical lidocaine and prilocaine cream (EMLA cream) may be applied to facilitate IV line placement. Blood will initially be drawn for hemoglobin,  $\beta$ HCG, and AST/ALT. In order to continue with the admission, girls must have a hemoglobin of  $\geq 11.5$  g/dL for non-African American subjects or a hemoglobin of  $\geq 11.0$  g/dL for African American subjects, negative  $\beta$ HCG, and normal AST/ALT. If the overnight portion of the study is to be done at a hotel, the hemoglobin,  $\beta$ HCG, and AST/ALT check will be done at the CRU 1-5 days prior to the overnight admission. Alternatively, subjects may come to the CRU early on the day of their admission before their scheduled admission time. The study team will be responsible for scheduling this with the subject. Frequent blood draws will begin at 1900 hr. Samples will be taken every 10 minutes. Most samples will be 0.75 mL, used to analyze levels of FSH and LH. 2.5 mL samples will be taken every 2 hours to analyze levels of estradiol, progesterone, testosterone, cortisol and DHEA. An additional 5 mL sample at 6 AM will be analyzed for fasting insulin, fasting glucose, lipids, estrone, SHBG, DHEA-S, androstenedione and a number of cytokines and adipokines, including adiponectin, leptin, resistin, PAI-1, IL-1b, IL-6, IL-8, TNFa, MCP-1, HGF and NGF. A formal "lights out" will occur at 2300 hr so that we may observe any nocturnal changes in hormonal secretion patterns. During blood sampling, activity (e.g., awake, sleeping) will be recorded by the nurse every 10 minutes. Additionally, periods of sleep will be estimated using wrist actigraphy (Motionlogger Basic-L; Ambulatory Monitoring, Inc.) The Motionlogger Basic-L is a watch-like device (that includes an accelerometer) that will be worn on the wrist by the research participant during the overnight admission. Q10 minute blood sampling will end at 0600 hr. There will be one final blood draw at 0700 hr. The subject will be offered meals at standard CRU meal times.

### **Day 1: Start Estradiol and Progesterone**

Starting the day of discharge from the first inpatient admission, subjects will be given oral estrogen (estrace, 0.5-1 mg once a day) and oral progesterone suspension (20 mg/ml, 25-100 mg) three times a day at 0700, 1500, and 2300 hr for seven days. If the 1500 dose is incompatible with school schedules, alternative dosing schedules can be arranged. Generally this will entail taking the afternoon dose immediately upon returning home from school without any change in the morning and evening dosing times. Dosages will be based on weight. The target mean plasma progesterone concentration is 2-8 ng/dL. Each subject will be

## **IRB-HSR#12632: Effect of Androgen Blockade on Sensitivity of the GnRH Pulse Generator to Suppression by Estradiol and Progesterone in Hyperandrogenic Adolescent Girls (JCM021)**

instructed to eat a small snack with the progesterone syrup. It has been observed that the absorption of progesterone is influenced by the presence or absence of food. Subjects will also be given oral iron supplementation at a dose of 1-2 mg/kg. Subjects weighing  $\leq$  38 kg will be given 325 mg of ferrous gluconate orally once a day and subjects weighing  $>38$  kg will be given 325 mg of ferrous gluconate orally twice a day to be taken until one month after study completion. Subjects will continue to take flutamide (250 mg PO BID for subjects  $\geq$  50 kg or 125 mg PO BID for subjects  $<$  50 kg).

### **Days 3, 5: Outpatient blood draws**

On study days 3 and 5, subjects will have blood drawn at 1700 hr (two hours after the 1500 hr progesterone dose) to check serum estrogen and peak progesterone levels.

### **Day 7: Second inpatient admission**

The second inpatient admission will begin on day 8. The procedure will be identical to the first inpatient admission. As with the first admission, blood will initially be drawn for hemoglobin,  $\beta$ HCG, and AST/ALT. In order to continue with the admission, girls must have a hemoglobin of  $\geq$  11.5 g/dL for non-African American subjects or a hemoglobin of  $\geq$  11.0 g/dL for African American subjects, negative  $\beta$ HCG, and normal AST/ALT. Subjects will discontinue flutamide, estrace, and progesterone after the completion of the second inpatient admission. They will continue to take iron supplements for one month after study completion.

### **Day 21: Outpatient blood draw.**

Subjects will return 14 days after hormonal study drugs have been discontinued for an outpatient blood draw for AST/ALT and  $\beta$ HCG.

### **Follow-up**

There is an optional 1 year follow up period. If the subject agrees to participate, she will complete follow-up questionnaires and/or phone interviews 3, 6 and 12 months after the study. These questionnaires/interviews will ask about the onset and frequency of menses and changes in hirsutism. Whenever possible we will also see the patients on 2-3 occasions during the 12 months to obtain blood for T, DHEA-S, E2, and P measurements (depending on cycle stage).

The PI will inform the subjects verbally of all incidental findings that are of clinical significance or are of questionable significance. A follow-up letter describing the finding should be provided to the subject with instructions to either show the letter to their PC or if the subject has no PCP, the subject should be instructed to make an appointment at UVa or at the Free Clinic

#### **2. Will any of the NON-RADIOLOGIC treatments/ procedures be done for research purposes only?**

Yes.►**IF YES, explain:** All procedures performed in this protocol are being done solely to answer a research question and generate generalizable knowledge.

#### **3. Will any RADIOLOGIC treatments/examinations be performed for research purposes only? No.**

#### **4. Will you be using viable embryos? No.**

#### **5. Will you be using embryonic stem cells? No.**

## Family History/Pedigree

**1. What kind of information is being sought?**

Family history (No questionnaire is being used)

**2. What identifiers will be recorded with the info (e.g. names, initials, relationship such as mother, father, brother, sister, random number)?**

Relationship

